**Figure 2: Prespecified Dose-Response Curves**

For a reference of different assumptions of STD of the change from baseline in UAS7 at Week 12, the sample sizes and the corresponding minimum power to detect a significant dose-response signal at a 1-sided 2.5% significance level are provided in [Table 3](#).

**Table 3: Sample Sizes and Minimum Power Across the 6 Prespecified Candidate Models Under Different Assumptions of Standard Deviation**

STD	Sample Size (Placebo:15 mg:45 mg:75 mg)	Minimum Power
11	100 (25:25:25:25)	0.85
12	116 (29:29:29:29)	0.84
13	136 (34:34:34:34)	0.85

### 3.4. Schedule of Assessments

Refer to Protocol Version 1 dated 07 MAR 2023 for a full description of all study procedures and assessment schedules for this study.

## 4. DATA HANDLING DEFINITIONS AND CONVENTIONS

### 4.1. Scheduled Study Evaluations and Study Periods

#### 4.1.1. Day 1

Day 1 is the date that the first dose of study drug is administered to participants.

#### 4.1.2. Study Day

If a visit/reporting date is on or after Day 1, then the study day at the visit/reporting date will be calculated as

$$\text{Day \#} = (\text{visit/reporting date} - \text{Day 1 date} + 1).$$

If the visit/reporting date is before Day 1, then the study day at the visit/reporting date will be calculated as

$$\text{Day \#} = (\text{visit/reporting date} - \text{Day 1 date}).$$

A study day of -1 indicates 1 day before Day 1.

#### 4.1.3. Baseline Value

For efficacy and safety evaluations during the PC period, baseline is the last nonmissing measurement obtained before or on the day of the first dose.

For participants who cross over into the EXT period, baseline is defined as follows:

- For efficacy evaluation during the EXT period, baseline is the last nonmissing measurement obtained before the first administration of placebo during the PC period.
- For safety evaluation during the EXT period, baseline is the last nonmissing measurement obtained before the first administration of study drug during the EXT period.

For participants who enter the post-treatment follow-up period, baseline for efficacy evaluation is defined as the last nonmissing measurement obtained on or before EOT2.

For participants who are on active drug throughout the study, efficacy and safety baseline is the last nonmissing measurement obtained before or on the day of the first dose.

When scheduled assessments and unscheduled assessments occur on the same day and the time of the assessment or time of first dose is not available, the following convention will be used to determine baseline:

- If both a scheduled and an unscheduled visit are available on the day of the first dose and the time is missing, use the scheduled assessment as baseline.
- If all scheduled assessments are missing on the day of the first dose and an unscheduled assessment is available, use the unscheduled assessment as baseline.

#### **4.1.4. Handling of Missing and Incomplete Dates**

In general, values for missing dates will not be handled unless methods for handling missing dates are specified in this section or relevant sections. The original reported dates collected in the eCRF should be used in all relevant listings. The following rules will be used for handling partial dates for analyses requiring dates.

When calculating the time since diagnosis of CSU, a partial CSU diagnosis date will be handled as follows in the calculation:

- If only the day is missing, then the first day of the month will be used.
- If both the month and day are missing, then 01 JAN of the year will be used.
- If the diagnosis date is completely missing, then the time since diagnosis will not be calculated.

When the date of the last dose in a specific period is used in deriving variables, such as duration of treatment or TEAE flag, a missing or partial date of the last dose will be handled as follows:

- If only the day is missing, then the earlier date of the last day of the month or the date that the participant discontinued treatment will be used.
- If both the month and day are missing, then the earlier date of 31 DEC of the year or the date that the participant discontinued treatment will be used.
- Otherwise, the date that the participant discontinued treatment will be used as the date of the last dose.

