6. STUDY TREATMENT

6.1. Study Treatments Administered

Table 7 presents the study treatment information. Participants will record study drug administration in an eDiary. Study drug administration and any interruptions and discontinuation of treatment will also be recorded in the eCRF. Further information regarding study drug administration is provided in Appendix C.

The COVID-19 global pandemic may present challenges to the normal conduct of this study, requiring the outline of potential mitigation strategies described in Appendix E.

Table 7: Study Treatment Information

Study treatment name:	Povorcitinib	Povorcitinib matching placebo
Mechanism of action:	JAK inhibitor	Not applicable
Dose formulation:	Tablet oral	Matching tablet
Unit dose strength(s) / dose level(s):	15 mg = 1 povorcitinib 15-mg tablet and 4 placebo tablets 45 mg = 3 povorcitinib 15-mg tablets and 2 placebo tablets 75 mg = 5 povorcitinib 15-mg tablets	Matching placebo = 5 tablets
Administration instructions:	Povorcitinib or matching placebo will be taken orally QD with water at approximately the same time each day unless otherwise instructed by site personnel. The study drug can be taken with or without food. Note: Dose will be administered at the study site during visits. Participants will withhold self-administration on the days of those visits.	
Packaging and labeling:	Povorcitinib will be provided as 15 mg tablets; placebo tablets will match the povorcitinib tablets in smell, taste, and appearance. Tablets will be packaged in blister cards. Each blister card will be labeled as required per country requirement.	
Storage:	Ambient (15°C-30°C/59°F-86°F).	
Status of treatment in participating countries:	Investigational	

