6.5.1. Compliance With Povorcitinib/Placebo

Compliance with study drug will be calculated by the sponsor based on the drug accountability (eg, tablet counts) documented by the site staff and monitored by the sponsor/designee. Participants will be instructed to bring all unused study drugs with them to the study visits in order for site personnel to conduct tablet counts to assess study drug accountability.

Compliance with study drug will be calculated for the PC and EXT periods based on the following:

Within the PC period:

- The first dose will occur on Day 1 (baseline).
- The last dose will occur on the day of the Week 12 visit or the day of the last study drug administration known to the investigator (or designee) as reported in the EDC for participants who prematurely discontinue study treatment or are lost to follow-up.

Within the EXT period:

- The first dose will occur the day after the Week 12 visit.
- The last dose will occur on the day of the Week 36 visit or the day of the last study drug administration known to the investigator (or designee) as reported in the EDC for participants who prematurely discontinue study treatment or are lost to follow-up.

Participants' compliance must be within 80% to 120% assessed at each study visit by the investigator (or designee). If outside of this range, it will be considered a Protocol deviation. Participants consistently noncompliant with the study drug may be withdrawn from the study. The decision on withdrawal will be made by the investigator after consultation with the sponsor, and relevant correspondence will be archived in the site study file.

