7.3. Lost to Follow-Up

A participant will be considered lost to follow-up if they repeatedly fail to return for scheduled visits and are unable to be contacted by the study site.

The following actions must be taken if a participant fails to return to the clinic for a required study visit:

- The site must attempt to contact the participant and reschedule the missed visit as soon as possible and counsel the participant on the importance of maintaining the assigned visit schedule and ascertain whether or not the participant wishes to and/or should continue in the study.
- Before a participant is deemed lost to follow-up, the investigator or designee must make every effort to regain contact with the participant (where possible, 3 telephone calls and, if necessary, a certified letter to the participant's last known mailing address or local equivalent methods). These contact attempts should be documented in the participant's medical record.
- Should the participant continue to be unreachable, they will be considered to have withdrawn from the study.

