### 6.4. Exposure

For participants in the Safety Population during the PC period and the EXT-Evaluable Population during the EXT period, as well as for participants who only received povorcitinib 15, 45, or 75 mg during the overall period, exposure to the study drug will be descriptively summarized by treatment group as follows:

- **Duration of treatment with study drug (days):** Date of last dose of study drug during the specific period – date of first dose of study drug during the specific period + 1.

The average daily dose of povorcitinib and total actual dose of povorcitinib administered will be summarized by treatment group as follows:

- **Average daily dose of povorcitinib (mg/day):** Total actual povorcitinib dose taken during the specific period (mg) / (duration of treatment with povorcitinib during the specific period [days] – number of interrupted days with povorcitinib during the specific period).
- **Total actual dose of povorcitinib administered (mg):** (Total number of tablets dispensed during the specific period – total number of tablets returned during the specific period) × 15 (mg/tablet) ×  $p_T$ ,

where  $p_T$  denotes the proportion of povorcitinib among the 5 tablets taken daily (ie,  $p_T = 0$  [0/5] for the placebo group, 1/5 for the povorcitinib 15 mg group, 3/5 for the povorcitinib 45 mg group, and 5/5 for the povorcitinib 75 mg group).

The total number of tablets dispensed and returned in each period is based on information entered on the Drug Accountability eCRF. Should the dispensed drug not be returned, the actual dose taken, starting from the dispense date of the unreturned drug, will be imputed by the dose taken per the Compliance eCRF.

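### SAP 4.1.4 sets no end-of-period limit on an imputed last-dose date, so a placebo-controlled-period last dose can be dated inside the extension

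*SAP*

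**What the plan says.** SAP 4.1.4 states its scope as "When the date of the last dose in a specific period is used in deriving variables, such as duration of treatment or TEAE flag", so it works one period at a time. It has three rules:

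- Day missing: "If only the day is missing, then the earlier date of the last day of the month or the date that the participant discontinued treatment".
- Month and day missing: "the earlier date of 31 DEC of the year or the date that the participant discontinued treatment will be used".
- Anything else: "Otherwise, the date that the participant discontinued treatment will be used as the date of the last dose".

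The only limits are calendar dates and the discontinuation date. Neither the Week 12 visit nor the first EXT dose is mentioned.

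Protocol 6.5.1 fixes the dates on which compliance is calculated. The last PC dose falls on the Week 12 visit day and EXT dosing starts the following day. For people who stop early or are lost to follow-up, the last dose is "the day of the last study drug administration known to the investigator (or designee) as reported in the EDC".

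SAP 6.4 computes duration from "Date of last dose of study drug during the specific period" minus the first dose in that period, plus 1. Average daily dose divides total milligrams by duration less interrupted days. SAP 6.5 uses the same days, times 5 tablets, as the compliance denominator. Total dose and tablets taken come from drug accountability, or from the Compliance eCRF if drug is not returned.

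**The concern.** Most people who finish the PC period go on to EXT. Any later treatment discontinuation they have falls in EXT. If the PC last-dose date is incomplete, a rule limited only by that later date can place the last PC dose inside EXT. The SAP would then contradict Protocol 6.5.1, and SAP 11.1, which lists changes to Protocol-defined analyses, does not mention it.

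The numerator of compliance is a tablet count and does not grow with the imputed date. The denominator does. The error therefore runs one way, provided discontinuation is not dated before the last dose: duration rises, while compliance and average daily dose fall.

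A second, softer issue concerns early stoppers. Their discontinuation may be dated some time after the last tablet, particularly when they are lost to follow-up, because Protocol 7.3 says "Before a participant is deemed lost to follow-up, the investigator or designee must make every effort to regain contact with the participant". Protocol 6.1 provides another source, "Participants will record study drug administration in an eDiary", which SAP 4.1.4 does not consult before it falls back on the discontinuation date.

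**Working it through.** The documents give no figure for this rule, so there is nothing to reproduce. The check applies the SAP formulas.

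**Formulas.** Duration = last dose − first dose + 1 (SAP 6.4). Compliance = 100 × tablets taken / (duration × 5), with no interruptions (SAP 6.5). Average daily dose = total mg / duration (SAP 6.4).

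**Assumptions.** First dose on Day 1; Week 12 visit on Day 85 (12 × 7 + 1; the ±3-day window gives Day 82 to 88); every tablet taken; no interruptions. Tablets taken = 85 × 5 = 425. In the 75 mg group, total dose = 85 × 75 = 6,375 mg.

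**PC completer who entered EXT, PC last-dose date incomplete:**

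| PC last dose set to | Duration (days) | Compliance | Average daily dose, 75 mg group |
|---|---|---|---|
| Day 85 (Protocol 6.5.1) | 85 | 425/425 = 100% | 6,375/85 = 75.0 mg |
| Day 113 (Week 16) | 113 | 425/565 = 75.2% | 6,375/113 = 56.4 mg |
| Day 169 (Week 24) | 169 | 425/845 = 50.3% | 6,375/169 = 37.7 mg |
| Day 253 (Week 36) | 253 | 425/1,265 = 33.6% | 6,375/253 = 25.2 mg |

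Across the visit window, the Day 113 row runs from 82/113 = 72.6% to 88/113 = 77.9%, and the Day 253 row from 82/253 = 32.4% to 88/253 = 34.8%.

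The Day 253 row treats the Week 36 end of treatment as a discontinuation date. SAP 6.2 separates completing from discontinuing treatment. On that reading a Week 36 completer has no discontinuation date, and the fallback returns nothing.

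**Only the day missing.** Month end adds at most 30 days (visit on the 1st of a 31-day month): duration 115, compliance 425/575 = 73.9%.

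**Overrun that matters.** A fully compliant participant falls below 80% once duration exceeds 85/0.80 = 106.25 days, that is, with an overrun of 22 days or more.

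**Arm level.** The number affected is an assumption. One such person among 34 with a 28-day overrun (Day 113) raises mean PC duration by 28/34 = 0.8 day and lowers mean compliance by 24.8/34 = 0.7 percentage point. With two, the figures are 1.6 days and 1.5 points.

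**Early stopper.** Suppose the true last dose is Day 43. The gap to the discontinuation date is not given in the documents, so a range is shown:

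| Gap (days) | Duration (days) | Compliance | General TEAE limit (last dose + 30) |
|---|---|---|---|
| 0 | 43 | 100% | Day 73 |
| 7 | 50 | 43/50 = 86.0% | Day 80 |
| 14 | 57 | 43/57 = 75.4% | Day 87 |
| 28 | 71 | 43/71 = 60.6% | Day 101 |

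**TEAE windows in SAP 9.2.1.** The PC window closes before the first EXT dose, or at the end of safety follow-up for those who do not enter EXT. The EXT window closes at EOT2 and the overall window at EOS. None uses the period's last-dose date. Only the general 30-day definition does.

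**The case against.** The best defence is that the trigger is rare. The Week 12 dose is given at the site on a dated visit, administration is recorded in the eCRF (Protocol 6.1), and Protocol 7.1.2 requires the last-dose date there when treatment stops. That stands, and it is the main reason the point is minor.

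It can also be said that SAP 6.4 speaks of a last dose within the period and that SAP 6.2 reports discontinuation by period, so a limit is implied. A sensible programmer might read it that way. But SAP 4.1.4 is the section that supplies the date when it is missing, and it names different limits. Two programmers could follow it and get different answers.

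Three stronger readings are tempting, and the documents do not support them:

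- **TEAE windows are lengthened.** SAP 4.1.4 names the TEAE flag as a use, so a reader might infer this. The PC, EXT and overall windows have their own end points. Only the general 30-day limit can move, and SAP 9.2.1 counts doubtful events as treatment-emergent by design.
- **The SAP contradicts Protocol 6.5.1 for everyone.** For early stoppers and those lost to follow-up, the Protocol relies on a date reported in the EDC. The SAP rule acts only when a date is missing or partial. The conflict is clear only for PC completers.
- **Exposure is overstated in every sense.** Only duration is. Total milligrams do not use the date, and average daily dose falls.

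A gap of weeks for those lost to follow-up is also not established. Protocol 7.3 describes the contact attempts but does not say which date is recorded as discontinuation.

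**Conclusion.** The point holds, and it is minor. As written, SAP 4.1.4 can return a PC last-dose date that lies in EXT, against Protocol 6.5.1. That is a rule with a wrong output, and more than a missing detail. For an affected participant the distortion is large: 113 days instead of 85 and 75% compliance instead of 100% at Day 113, and as low as 34% if the date reaches Day 253. These figures assume full intake, no interruptions and a Week 12 visit on Day 85.

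Across an arm the effect is small under the assumed one or two cases, and the documents give no frequency. It touches descriptive summaries of duration, average daily dose and compliance. No efficacy endpoint or analysis population depends on it. The 80% to 120% compliance range in Protocol 6.5.1 is assessed by the investigator at each visit, so this imputation does not by itself create a protocol deviation. The missing limit matters only for the PC period, because EXT is the last treatment period. For early stoppers, overstatement is possible but unquantified.

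**What to change.** Amend SAP 4.1.4 in three respects:

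- For participants who completed the PC period, impute a missing PC last-dose date as the Week 12 visit date.
- Cap every imputed PC date, including the month-end and 31 December cases, at the day before the first EXT dose.
- For early stoppers and those lost to follow-up, use the last administration recorded in the EDC or eDiary where one exists, and only then the discontinuation date.

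The cost is one SAP paragraph and a small programming change on data already collected. Reported PC duration becomes shorter, and compliance and average daily dose higher, for the few participants with incomplete dates. Nothing else in the analysis changes.

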## **4.2. Variable Definitions**

The following variable will only be calculated if not reported on the eCRF.

### **4.2.1. Body Mass Index**

Body mass index will be calculated as follows:

$$\text{Body mass index (kg/m}^2\text{)} = [\text{weight (kg)}] / [\text{height (m)}]^2.$$

#### 4.2.2. Prior and Concomitant Medication

Prior medication is defined as any nonstudy medication started before the first dose of study drug.

For the PC period, concomitant medication is defined as any nonstudy medication that is started accordingly:

- Before the date of first administration of povorcitinib or placebo during the PC period and is ongoing or ends on/after the date of first study drug administration during the PC period
- or
- On/after the date of first administration of povorcitinib or placebo during the PC period and before the date of first administration of povorcitinib during the EXT period for participants who enter the EXT period

For the EXT period, concomitant medication is defined as any nonstudy medication that is started accordingly:

- Before the date of first administration of povorcitinib during the EXT period and is ongoing throughout the study or ends on/after the date of first study drug administration during the EXT period
- or
- On/after the date of first administration of povorcitinib during the EXT period

A prior medication could also be classified as both prior and concomitant medication if the end date is on or after the first dose of povorcitinib or placebo during the PC period. In the listing, it will be indicated whether a medication is only prior, only concomitant, or both prior and concomitant.

For the purposes of analysis, all medications will be considered concomitant medications unless the medications can unequivocally be defined as not concomitant.

## **5. STATISTICAL METHODOLOGY**

### **5.1. General Methodology**

Unless otherwise noted, SAS® software (SAS Institute Inc, Cary, NC; v9.1 or later) will be used for the generation of all tables, graphs, and statistical analyses. Descriptive summaries for continuous variables will include, but not be limited to, the number of observations, mean, STD, median, minimum, and maximum. Descriptive summaries for categorical variables will include the number and percentage of participants in each category.

### **5.2. Treatment Groups**

Table summaries, unless otherwise indicated, will present data by treatment group. The results will be summarized and presented separately for the PC period, EXT period, post-treatment period, and overall period (for safety only) unless otherwise specified.

For the PC period, the treatment groups will be placebo and povorcitinib 15, 45, and 75 mg.

For the EXT period and the post-treatment follow-up period, the treatment groups will be as follows:

- Placebo to povorcitinib 15 mg
- Placebo to povorcitinib 45 mg
- Placebo to povorcitinib 75 mg
- Povorcitinib 15 mg
- Povorcitinib 45 mg
- Povorcitinib 75 mg

For the overall period, the treatment groups will be povorcitinib 15, 45, and 75 mg.

### **5.3. Analysis Populations**

#### **5.3.1. Full Analysis Set Population**

The FAS includes all randomized participants who received at least 1 dose of study drug. Treatment groups for this population will be determined according to the treatment they were assigned at the time of randomization.

The FAS will be used for the summary of demographics, baseline characteristics, and participant disposition and for the analyses of all efficacy data from the PC period and the overall period.

#### **5.3.2. Safety Population**

The Safety Population includes all participants who received at least 1 dose of study drug. Treatment groups for this population will be determined according to the actual treatment the participant received regardless of assigned study drug treatment.

All safety analyses for the PC and overall period will be conducted using the Safety Population.

### 5.3.3. Extension-Evaluable Population

All analyses for the EXT period will be conducted with the EXT-Evaluable Population, which includes all participants who received at least 1 dose of povorcitinib during the EXT period.

### 5.3.4. Post-Treatment–Evaluable Population

All analyses for the post-treatment period will be conducted with the Post-Treatment–Evaluable Population, which includes all participants who agree to be observed during the post-treatment period.

## 6. BASELINE, EXPOSURE, AND DISPOSITION

[Appendix A](#) provides a list of data displays. Sample data displays are included in a separate document.

### 6.1. Demographics, Baseline Characteristics, and Disease History

The demographics, baseline characteristics, and disease history will be summarized by treatment groups and overall.

